2.2 STUDY OBJECTIVES

This study is to describe the safety and efficacy of Sayana® during the usual care setting.

The objective can be specified as below:

- *To detect serious adverse events and adverse drug reactions.*
- *To detect unexpected adverse events and adverse drug reactions that are not included in precaution of local product document.*
- *To observe already known adverse drug reactions.*
- *To observe non-serious adverse drug reactions.*
- *To detect other information on safety and efficacy.*

3 INTERIM ANALYSES

As required by MFDS regulations, the periodic report should be submitted to MFDS every 6 months for the first two years and then annual report should be submitted to MFDS for the third, fourth and fifth year. The final report should be submitted in the sixth year. Interim analysis will be performed in time for the report submission.

[figure not shown]
However, according to re-examination period extension, additional annual reports will be submitted to MFDS in the sixth and seventh year and the final report will be submitted in the eighth year.

This Statistical Analysis Plan (SAP) details the analyses and outputs to be produced for the interim and final analyses.

The analyses for types of medical history(past/present disease), types of concomitant medications, any clinically significant abnormal finding from laboratory test reported as an AE (if necessary and data are applicable), the classification of AE by preferred term according to severity, action, seriousness, outcome, causal relationship to Sayana® and other causal relationship regarding occurred AE and estimation of 95% confidence interval for AEs by baseline characteristics, System Organ Classes and Preferred Term of Serious AE/Serious ADR, unexpected AE/ unexpected ADR according to the frequency of AEs in the prescribing information, Basic Results Tables will be performed for the re-examination report (i.e. final report) only.

Note: Although it was planned that interim analyses would be performed for the report submission to the MFDS annually, interim analyses were not performed for the annual reports for the first one year. The first interim analysis will be performed once this SAP is finalized.

PFIZER CONFIDENTIAL

4 HYPOTHESES AND DECISION RULES

Not Applicable

5 ANALYSIS SETS/ POPULATIONS

All subjects entered into this study will be evaluated as to whether they are eligible to be in the Safety Analysis Set and the Efficacy Analysis Set.

All subjects excluded from the Safety Analysis Set will be counted for as part of the subject enrolled in the Clinical Study Report. Any adverse events reported for subjects excluded from the Safety Analysis Set will also be described.

5.1 SAFETY ANALYSIS SET

Subject who have been administered Sayana® at least once will be included in the safety analysis set.

[figure not shown]
The following exclusions from the Safety Analysis Set are to ensure that the subjects who are not providing data to the analyses but have some record of treatment do not over-inflate the denominator for the analyses.

The following cases are excluded from the safety analysis set:

- Subjects who have taken Sayana® prior to the contract date
-
- Subjects who didn't receive Sayana® for this study
- Follow-up failure: Subjects for whom adverse event status (Adverse Events status is unknown or missing in CRF) could not be established
- Subjects who violate the inclusion/exclusion criteria (see section 2.1)
- Subjects who were prescribed for other indications except indications in the local product document:
 - [Indications]
 - Prevention of pregnancy in women of child bearing potential
 - Management of endometriosis associated pain
- Subjects who violate the dosage
 - [Dosage]
Sayana® is injected under the skin into the front upper thigh or abdomen every 3 months (12 to 14 weeks).

Unless specified otherwise, safety summaries and analyses will be presented for the safety analysis set.

PFIZER CONFIDENTIAL

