**Figure 1. Data Management Flow Chart**

**Figure 2. Data Validation Flow Chart**

## 7.7. Data analysis

### 7.7.1. Assessment of Safety and Effectiveness Parameters

#### 7.7.1.1. Analysis Populations

All analyses will be performed on the safety population, defined as those patients who took at least one dose of study medication.

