5.2 EFFICACY ANALYSIS SET

Subject who have been administered Sayana® at least once and evaluated upon its related efficacy endpoints at least once will be included in the efficacy analysis set. The efficacy analysis set is a subset of the safety analysis set.

The following cases are excluded from the efficacy analysis set:

- Subjects excluded from safety analysis set listed in section 5.1
- If the purpose of administration was the prevention of pregnancy in women of child bearing potential, subjects whose check either pregnant or not pregnant at evaluation date on the CRF are not completed
- If the purpose of administration was management of endometriosis-associated pain, subjects whose record VAS score at baseline or evaluation date on the CRF are not completed

Unless specified otherwise, statistical analysis on efficacy parameters will be performed on the efficacy analysis set.

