8.2.1.4 Adverse Events by Preferred Terms (AEs/ADRs/SAEs)

All AEs recorded in CRFs will be classified into the system organ class (SOC) and the terms of AE will be coded according to the classification of AEs in 'Precautions of Use' in the local product document of Sayana®/WHO-ART/MedDRA order. All AEs, except for those with causality of adverse event to the study drug classified as 'Unlikely', will be considered as AEs whose causal relationship to the study drug cannot be excluded (hereinafter "Adverse Drug Reaction (ADR)").

- The number and percentage of AE will be presented overall and by preferred term. This will be repeated by:

PFIZER CONFIDENTIAL

- severity
- action
- seriousness
- outcome
- causal relationship to Sayana®
- other causal relationship regarding occurred AE

- The number of subjects and the number of unexpected AE/ADR, SAE/Serious ADR (SADR), unexpected SAE/SADR, AE/ADR will be calculated according to the preferred terms. Also, the proportion of subjects to whom AE occurred will be estimated. In re-examination report, SAE/SADR and unexpected AE/unexpected ADR in accordance with preferred terms will be presented respectively according to the frequency categories of adverse events in the approved local label.
- The subjects with Serious AE, Unexpected AE, Unexpected Serious AE, AE of G eriatric, kidney disorder, liver disorder will be listed for safety analyses sets.
- For subjects excluded from the safety analysis set*, the number of subjects and the number of unexpected AE/ADR, SAE/Serious ADR (SADR), unexpected SAE/SADR, AE/ADR will be calculated according to the preferred terms. Also, the proportion of subjects to whom AE occurred will be estimated.

* Subjects excluded from safety analysis set: Subjects excluded from safety analysis set except for 'subjects who didn't receive Sayana®' and 'subjects for whom adverse event status (Adverse Events status is unknown or missing) could not be established'.

Note: Unexpected AEs/ADRs will be classified by medical review and with reference to the local product document. Terms already included in the local product document are classified as 'expected'. All other terms that are not included in the local product document will be classified as 'unexpected'. These can't be classified without the local product document.

- For subjects excluded from safety analysis set, Serious AE, unexpected AE, Unex pected Serious AE will be listed.

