8.2.2 Efficacy Analysis

The cumulative percent of patients who become pregnant by month 6 will be calculated as $100*(1 - \text{Kaplan-Meier curve at month 6})$, where the Kaplan-Meier (KM) method for estimating survival function will be applied to time-to-pregnancy. Patients who did not become pregnant will be censored at the time of their last follow-up. The KM method will also be used to calculate a 95% confidence interval for this cumulative percent at month 6.

[figure not shown]
[figure not shown]
The rate of pregnancies per 100 person-years of follow-up will be summarized by a 95% confidence interval.

For the rate of pregnancies per 100 person-years of follow-up defined as major events, incidence rate will be calculated as follows:

$100 \times (\text{total number of patients with effectiveness endpoint}) / (\text{total person-years of patients included in the effectiveness analysis set})$ where total person-years is equal to (last evaluation date of outcome - first date of administration +1)/365.25 for all patients in the effective analysis set

The difference between the visual analogue scale (VAS) endometriosis pain scores measured at each visit and the measurement taken before the administration of Sayana[®] will be analyzed using paired t-test.

PFIZER CONFIDENTIAL

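### The SAP drops dosage violators from every pregnancy estimate, while the protocol analyses everyone with at least one dose; the departure is unexplained and the violation has no operational rule

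*SAP*

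**What the plan says.** Protocol 7.7.1.1 states: "All analyses will be performed on the safety population, defined as those patients who took at least one dose of study medication". It lists no exclusions.

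SAP 5.1 starts from the same rule and then lists exclusions, one of which is "Subjects who violate the dosage". A dosage line beneath it gives the route (under the skin), the site (front upper thigh or abdomen) and the interval (every 3 months, 12 to 14 weeks). The reason given for the whole list is that "subjects who are not providing data to the analyses but have some record of treatment do not over-inflate the denominator for the analyses".

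SAP 5.2 carries the exclusions over: "The efficacy analysis set is a subset of the safety analysis set". Efficacy parameters are analysed in that set by default. SAP 8.2.2 divides by the "total person-years of patients included in the effectiveness analysis set" and names no other population for the 6-month Kaplan-Meier percent.

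Excluded subjects are not ignored. SAP 5 counts them among those enrolled and adds: "Any adverse events reported for subjects excluded from the Safety Analysis Set will also be described". SAP 8.2.1.4 plans tables by preferred term: "For subjects excluded from the safety analysis set*, the number of subjects and the number of unexpected AE/ADR", and so on for the other event classes.

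**The concern.** Protocol 6 sets out to describe safety and effectiveness in usual care, and protocol 7.1 leaves visit timing to the investigator. Early, late or missed repeat injections are part of usual care. A pregnancy estimate without the women who had them describes on-schedule use, which is a different quantity from the one the protocol population implies.

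Whether a woman kept to the interval is known only after follow-up has begun. Membership of the analysis set therefore depends on events during the period in which pregnancy is counted. The pregnancy counts may be very low, so moving one or two women in or out could change the reported point estimate. The adverse event denominator also differs from the one in the protocol.

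**Working it through.** **1. Who is removed.** The dosage line gives route, site and interval. It does not say whether an early, late or missed repeat injection counts, and it says nothing about the amount injected. The SAP's own tables do not settle the matter. SAP 8.2.1.1 and 8.2.1.3 split adverse events in the safety set by number of injections (1, 2, 3, 4, more than 4) and by dose per injection, including an Other category.

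- The category for 1 injection suggests, without stating it, that single-injection women stay in.
- Over 26 weeks, injections 12 weeks apart fall at weeks 0, 12 and 24, which makes three. At 14 weeks apart they fall at weeks 0 and 14, which makes two. Within 6 months, four or more injections would need a shorter interval than the dosage line gives.
- The set therefore has rows for women whom its own exclusion may remove. Two programmers could build different sets from this text.

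**2. Whether the stated reason fits.** It concerns subjects who provide no data. A woman injected off-interval, followed and checked for pregnancy provides an outcome and person-time.

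**3. Direction.** Let D be all pregnancies, k those in excluded women, PY the total person-years and f the share of person-time excluded.

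- Full rate = 100 × D / PY
- Restricted rate = 100 × (D − k) / (PY × (1 − f))
- Restricted ÷ full = (1 − k/D) / (1 − f)

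The restricted rate is lower only if k/D > f, unchanged if k/D = f, and higher if k/D < f. If late injection goes with pregnancy, the rate falls. If women who become pregnant before a second injection are kept as single-injection users, while non-pregnant late attenders are removed, it rises.

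**4. Illustrative size.** The plan has no figure of its own to reproduce: the 600 in protocol 7.5 is a regulatory minimum with no pregnancy rate behind it. The documents give no number of contraception users, dosage violators or pregnancies.

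Assumptions: 600 contraception users × 0.5 year = 300 PY, and 20% of women and person-time excluded, leaving 240 PY (range 10% to 30%, leaving 270 to 210 PY). For d pregnancies, the exact Poisson 95% limits are χ²(0.025, 2d)/2 (0 if d = 0) and χ²(0.975, 2d + 2)/2, each divided by PY and multiplied by 100.

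| Case | With dosage violators, 300 PY | Without, 240 PY | Range for 10% to 30% excluded |
|---|---|---|---|
| (a) No pregnancies | 0 (0 to 1.23) | 0 (0 to 1.54) | upper limit 1.37 to 1.76 |
| (b) One, in a retained woman | 0.33 (0.01 to 1.86) | 0.42 (0.01 to 2.32) | rate 0.37 to 0.48 |
| (c) Three, two in excluded women | 1.00 (0.21 to 2.92) | 0.42 (0.01 to 2.32) | rate 0.37 to 0.48 |

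In (c), with no earlier loss to follow-up, the 6-month percent goes from 3/600 = 0.50% to 1/480 = 0.21%. With 200 users (100 PY) and no pregnancies, the upper limit goes from 3.69 to 4.61 at 20% excluded.

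**The case against.** The strongest reply has four parts.

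- **The SAP is allowed to differ.** Protocol 7.7.2.2 lets the SAP modify the plan, and 7.9 says the SAP follows an MFDS guideline, which may contain the reason. Protocol 7.2 and 7.2.1 also tie enrolment to the local product document. This stands as far as it goes. A reader might infer a protocol breach, but the documents do not support that. The amendment duty in 7.7.2.2 concerns major changes to primary endpoints, and no endpoint is labelled primary. Permission is still not a reason, and nothing in these passages prevents an added estimate.
- **The scope is not wholly undefined.** This stands. There is a dosage line, and the category for 1 injection suggests that single-injection women are retained, so the excluded group may be small. What is missing is the operational rule.
- **The pregnancies are not hidden.** This stands in part. Protocol 9.1 requires pregnancy exposure and lack of efficacy on the case report form, and 9.2.1 lists lack of efficacy as an example of an adverse event. A contraceptive failure in an excluded woman could therefore appear in the excluded-subject tables if recorded as an adverse event. It would still enter no Kaplan-Meier percent or person-year rate.
- **The effect is modest and the inputs are unsourced.** This stands. The 600 minimum covers both indications, so 600 contraception users is a high assumption, and the 10% to 30% share has no source. Protocol 5 cites zero pregnancies in two trials under perfect use. If that held here, only the upper limit would widen.

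**Conclusion.** The mismatch between protocol 7.7.1.1 and SAP 5.1, 5.2 and 8.2.2 is certain from the text. It is an unreconciled and unexplained departure, with no operational rule for the violation, and it should be fixed.

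The size and sign of any bias are unknown. A reader might infer that the exclusion must flatter the product. The documents do not show that: the rate falls only if excluded women hold a larger share of pregnancies than of person-time, and case (b) moves the other way. Even in case (c), which assumes two of three pregnancies among 20% of the women, the intervals overlap, so the effect is on the point estimate. All the figures rest on the assumed number of users, full 6-month follow-up and the assumed share excluded.

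**What to change.** 1. Reconcile the two population definitions and give the reason for the exclusion.
2. State in the SAP which departures count as a dosage violation for the analysis sets, including how a single injection with no repeat is classed. This is an analysis definition only and sets no clinical rule.
3. Add the 6-month Kaplan-Meier percent and the person-year rate in the efficacy set's contraception users plus women excluded only for a dosage violation who have a pregnancy assessment. Show them beside the planned estimates.
4. Keep the other SAP 5.1 and 5.2 exclusions in the added analysis: use before the contract date, eligibility violations (including baseline pregnancy and women not at risk) and no pregnancy check. Putting back everyone ever dosed would add new bias. SAP 8.2.2 counts time from first administration, so if 60 of 600 women each brought one unobserved earlier year (assumed), three pregnancies would give 100 × 3/360 = 0.83 instead of 1.00. One woman already pregnant at first injection, counted as a failure, would turn 0 into 100 × 1/300 = 0.33.
5. Add the overall adverse event incidence with dosage violators of known adverse event status included.
6. Report how many women and how many pregnancies each exclusion removes.

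The cost is a SAP revision and one extra set of tables. Injection dates, pregnancy checks and, for pregnant women, the last menstrual period are already collected under protocol 7.3.1.5. The pregnancy rate may look less favourable.

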5.2 EFFICACY ANALYSIS SET

Subject who have been administered Sayana® at least once and evaluated upon its related efficacy endpoints at least once will be included in the efficacy analysis set. The efficacy analysis set is a subset of the safety analysis set.

The following cases are excluded from the efficacy analysis set:

- Subjects excluded from safety analysis set listed in section 5.1
- If the purpose of administration was the prevention of pregnancy in women of child bearing potential, subjects whose check either pregnant or not pregnant at evaluation date on the CRF are not completed
- If the purpose of administration was management of endometriosis-associated pain, subjects whose record VAS score at baseline or evaluation date on the CRF are not completed

Unless specified otherwise, statistical analysis on efficacy parameters will be performed on the efficacy analysis set.

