### 7.3.1.5. Administrative Status for Sayana®

Sayana® is provided by the investigator's prescription, and Pfizer Korea will not provide Sayana® for this study.

Record the following with regard to administrative status of Sayana®.

- Date of administration: Record the date of each Sayana® therapy (year/ month/day).
- Dose: Record the dose (ml).
- Outcome of administration:  
Record the evaluation date. If the purpose of administration was the prevention of pregnancy in women of child bearing potential, check either pregnant or not pregnant with the method of pregnancy check. If the subject is pregnant, record the first day of last menstrual period to collect the time to pregnancy. (At the time of first Sayana® administration, investigator must ensure the subject is non-pregnant. Also if a sexually active subject is having regular menstrual cycle and was previously not being administered with other contraceptive agent (therefore is having normal menstrual cycle), investigator must ensure that the first Sayana® injection is within 5 days of the subject's normal menstrual cycle. If the subject was previously being administered with other contraceptive agent(s) and is not having normal menstrual cycle, investigator must ensure that the subject is not pregnant by a method decided by the investigator).

If the purpose of administration was management of endometriosis-associated pain, visual analogue scale scores recorded by the subject.

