##### Exposure during pregnancy

An exposure during pregnancy (EDP) occurs if:

1. A female becomes, or is found to be, pregnant either while receiving or having been exposed to (e.g., environmental) Sayana®, or the female becomes, or is found to be, pregnant after discontinuing and/or being exposed to Sayana® (maternal exposure).

An example of environmental exposure would be a case involving direct contact with a Pfizer product in a pregnant woman (e.g., a nurse reports that she is pregnant and has been exposed to chemotherapeutic products).

2. A male has been exposed, either due to treatment or environmental exposure to Sayana® prior to or around the time of conception and/or is exposed during the partner pregnancy (paternal exposure).

As a general rule, prospective and retrospective exposure during pregnancy reports from any source are reportable irrespective of the presence of an associated AE and the procedures for SAE reporting should be followed.

If a study participant or study participant's partner becomes, or is found to be, pregnant during the study participant's treatment with Sayana®, this information must be submitted to Pfizer, irrespective of whether an adverse event has occurred using the NIS AEM Report Form and the EDP Supplemental Form.

In addition, the information regarding environmental exposure to Sayana® in a pregnant woman (e.g., a subject reports that she is pregnant and has been exposed to a cytotoxic product by inhalation or spillage) must be submitted using the NIS AEM Report Form and the EDP supplemental form. This must be done irrespective of whether an AE has occurred.

Information submitted should include the anticipated date of delivery (see below for information related to termination of pregnancy).

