7 HANDLING OF MISSING VALUES

No imputation of missing data will be performed. Missing or incomplete data will be excluded from the analyses.

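### SAP 5.2 drops a contraception user whose pregnancy check is blank, with no exception for a pregnancy documented elsewhere in the study, so a known failure could be lost from the effectiveness estimates

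*SAP*

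**What the plan says.** SAP 5.2 admits to the efficacy set women who had at least one dose and were "evaluated upon its related efficacy endpoints at least once will be included in the efficacy analysis set". It then removes, among those treated for contraception, "subjects whose check either pregnant or not pregnant at evaluation date on the CRF are not completed". No exception is given. The same section states that, unless specified otherwise, "statistical analysis on efficacy parameters will be performed on the efficacy analysis set". SAP 7 adds: "No imputation of missing data will be performed. Missing or incomplete data will be excluded from the analyses".

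The field in question is described in Protocol 7.3.1.5, where the investigator is to "check either pregnant or not pregnant with the method of pregnancy check" and, if the woman is pregnant, to record the first day of her last menstrual period so that time to pregnancy can be derived.

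Pregnancies also enter the study by another route. The table in Protocol 9.1 requires every exposure during pregnancy and every lack of efficacy to be recorded on the CRF and reported to the sponsor's safety group within 24 hours. Under Exposure during pregnancy in Protocol 9.2.3, when a participant is found to be pregnant during treatment, "this information must be submitted to Pfizer, irrespective of whether an adverse event has occurred", using the NIS AEM form and the exposure-during-pregnancy (EDP) supplement.

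SAP 8.2.2 defines the pregnancy rate as 100 times the "total number of patients with effectiveness endpoint" divided by the person-years of the effectiveness set. The Kaplan-Meier percentage at month 6 falls under the same rule on analysis sets. Protocol 7.7.1.1 sets a wider population: "All analyses will be performed on the safety population, defined as those patients who took at least one dose of study medication".

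**The concern.** The exclusion looks only at one CRF check. The study can hold a documented pregnancy, on a safety page of the same CRF or on an EDP form, while the SAP treats that woman's effectiveness outcome as missing.

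The situation is plausible. Protocol 7.3.1 fixes no visit schedule. The follow-up call in Protocol 7.2 is meant to collect adverse events and concomitant medication, and pregnancy status is not named. A woman who does not return but mentions a pregnancy on that call has a known adverse-event status, so she is not a follow-up failure under SAP 5.1. Her outcome check may still be blank.

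Very few pregnancies are expected: Protocol 5 cites none among 1,787 women in two earlier trials under perfect use. With counts this low, one lost event can separate a report of zero pregnancies from a report of one.

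**Working it through.** **Step 1. What happens to her under the text.** SAP 5.2 does not say whether one blank check or only a complete absence of checks triggers exclusion. There are two cases.

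- *She is excluded.* She leaves both the numerator and the person-years of the rate, and she leaves the Kaplan-Meier risk set.
- *An earlier not-pregnant check keeps her in.* Nothing in SAP 8.2.2 says that a pregnancy known only from a safety record is an endpoint. She would then be censored at her last follow-up as a non-event.

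The event is lost in both cases.

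**Step 2. Inputs.** The documents contain no calculated figure to reproduce. The 600 in Protocol 7.5 is a regulatory minimum, and Protocol 7.7.2 tests no hypothesis. From the documents: six months of observation (Protocol 7.1), the rate formula (SAP 8.2.2) and a Poisson interval (Protocol 7.7.2.2). Assumed, because the documents do not give them: 600 or 300 contraception users, 0.5 person-years for a woman who does not become pregnant, 0.25 for one who does, and one to three pregnancies.

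**Step 3. Formulas.** Rate = 100 × k / PY. Exact 95% limits for the count: lower χ²(0.025; 2k)/2 (zero when k = 0), upper χ²(0.975; 2k + 2)/2, each × 100 / PY. With no early censoring, the Kaplan-Meier percentage is 100 × k/n.

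**Step 4. Results, per 100 person-years.**

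| Users | True pregnancies | Lost | All counted | After the loss |
|---|---|---|---|---|
| 600 | 1 | 1 | 100 × 1/299.75 = 0.33 (0.01 to 1.86) | 0/299.5 = 0 (upper limit 1.23) |
| 600 | 3 | 1 | 100 × 3/299.25 = 1.00 (0.21 to 2.93) | 100 × 2/299.0 = 0.67 (0.08 to 2.42) |
| 300 | 1 | 1 | 100 × 1/149.75 = 0.67 (0.02 to 3.72) | 0/149.5 = 0 (upper limit 2.47) |
| 300 | 3 | 1 | 100 × 3/149.25 = 2.01 (0.41 to 5.87) | 100 × 2/149.0 = 1.34 (0.16 to 4.85) |

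With one pregnancy, the Kaplan-Meier percentage goes from 1/600 = 0.17% (or 1/300 = 0.33%) to 0%. At zero events the Greenwood interval has zero width, so the output would show no uncertainty.

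**Step 5. Blanks in women who are not pregnant.** Excluding one such woman removes 0.5 person-years. With one pregnancy among 600 users, the rate moves from 100/299.75 = 0.3336 to 100/299.25 = 0.3342. In the three-pregnancy row for 600 users, the rate after the loss returns to its full value only if person-years fall to 2 × 299.25/3 = 199.5. That is 99.5 fewer than 299.0, or 199 further exclusions. A lost event therefore weighs far more than a lost non-event.

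**The case against.** The strongest reply is that a blank check beside a recorded pregnancy should not survive data cleaning. Protocol 9.1 puts the exposure on the CRF as well as on the safety form, so the blank would be an inconsistency within one CRF and an obvious query. Protocol 7.8 requires a quality check of all items before lock, Protocol 8.2 asks for every effort to document subject outcome, and the data management and validation flow charts in Protocol 7.6 are not readable here. This stands in part. Queries may fill some boxes, and a reconciliation rule cannot be ruled out. However, no readable section states one, and the SAP rule says nothing about what to do if the box stays blank.

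A reader might infer that the rule systematically removes failures. The documents do not support that. The rule is neutral on its face and excludes pregnant and non-pregnant women alike. The frequency of blanks by outcome is unknown, and excluding non-pregnant women raises the rate slightly. What can be said is narrower: each known pregnancy that is discarded lowers the estimates.

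A reader might also infer that the pregnancy disappears from the study. It does not. It would still reach the safety group, and because Protocol 9.2.1 lists lack of efficacy among its examples of adverse events, it could also appear in the adverse event outputs. Only the effectiveness result is affected.

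Finally, the narrower SAP population could be read as a protocol breach. Protocol 7.7.2.2 allows the SAP to modify the planned analyses, so the difference from Protocol 7.7.1.1 needs reconciling but is not in itself a violation.

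**Conclusion.** The point holds as a possibility created by the text. SAP 5.2 makes the pregnancy endpoint depend on one CRF check, while the protocol requires other records that can establish the same outcome. Following the rule as written can drop or censor a known contraceptive failure.

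If it happens to the only pregnancy, the reported rate becomes zero: from 0.33 per 100 person-years with 600 users, or from 0.67 with 300. If it happens to one of three, a third of the rate is lost. These sizes rest on the assumed numbers of users, follow-up and pregnancies; the 600 minimum is not split by indication. The intervals before and after overlap widely, and the study is descriptive, so no test result turns on this. What changes is the headline estimate. The gap should be closed, but the documents do not show that it will bias the result.

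**What to change.** In SAP 5.2 and 8.2.2:

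- Count a pregnancy documented in any study source (outcome check, CRF safety pages, EDP or lack-of-efficacy report) as an event, and keep that woman in the efficacy set whatever the outcome check shows.
- Define her event date and person-time. SAP 8.2.2 ends person-time at the last outcome evaluation, which she may not have, and a blank outcome page may also lack the last menstrual period. Use the last menstrual period or conception date from the CRF or EDP form, or the report date if neither is available.
- List separately any pregnancy in a dosed contraception user excluded under SAP 5.1. The efficacy set is a subset of the safety set, so a change to 5.2 alone does not reach women dropped for unknown adverse-event status or a dosage violation.
- Require reconciliation of the CRF outcome with EDP and lack-of-efficacy reports before database lock.
- Reconcile the SAP 5.2 set with Protocol 7.7.1.1, which places all analyses on patients with at least one dose.

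The cost is SAP wording and one listing. The pregnancy rate may come out less favourable. No visit, procedure or treatment decision changes.
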